12.4.3 Case Report Forms and Source Documentation

The investigator must make study data accessible to the site monitor, to other authorized representatives of the IND Sponsor (or designee) and to the appropriate regulatory authority inspectors.

12.4.4 Retention of Study Documents

According to ICH E6, Section 4.9, all CRFs, as well as supporting paper and electronic documentation and administrative records, must be retained for at least 2 years after the last approval of a marketing application and until there are no pending or contemplated marketing applications, or at least 2 years have elapsed since the formal discontinuation of clinical development of an individual product. Longer retention periods may apply.

Audit trails for electronic documents will be retained for a period at least as long as that required for the subject electronic records to which they pertain. The investigator will retain either the original or a certified copy of audit trails.

12.4.5 Data Confidentiality and Subject Anonymity

All information about the nature of the proposed investigation provided by the IND Sponsor or their representative to the investigator (with the exception of information required by law or regulations to be disclosed to the IRB, the subject or the appropriate regulatory authority) must be kept in confidence by the investigator.

The anonymity of participating subjects must be maintained. Subjects will be identified by their initials and an assigned subject number on CRFs and other documents retrieved from the site or sent to the IND Sponsor, study monitor, Incyte, regulatory agencies, or central laboratories/reviewers. Documents that identify the subject (e.g., the signed ICF) will be maintained in strict confidence by the investigator, except to the extent necessary to allow auditing by the appropriate regulatory authority, IND Sponsor or their representative.

13. STATISTICAL CONSIDERATIONS

13.1 Study Design/Endpoints

Sample Size calculation and justification

Simon's two-stage optimal design will be used ¹⁸. The null hypothesis that the true disease control rate at 4 months is 5% will be tested against a one-sided alternative of 30% disease control rate at 4 months. In the first stage, 7 patients will be accrued. If there are zero patients with disease control by 4 months, the study will be stopped. Otherwise, 14 additional patients will be accrued for a total of 21 patients. The null hypothesis (disease control rate of 5%) will be rejected if 3 or more patients with disease control at 4 months are observed in stage 1 and 2 combined. This design yields a type I error rate of 0.064 (target type I error 0.1) and power of 90% when the true disease control rate is 30%. The probability of stopping the trial early for futility is 70% if the true DCR is 5%.

We plan to enroll 25 subjects to ensure 21 would be evaluable for DCR. As this is a rare tumor subtype patients will be recruited at several sites including Johns Hopkins Hospital, Memorial Sloan Kettering Cancer Center and the Mayo Clinic. We do not anticipate any difficulties in trial enrollment. We expect an accrual rate of at least 2 patients per month across the sites, completing trial enrollment in 12 months.

Patients are evaluable for DCR if they receive at least one dose of retifanlimab, and have at least one post-baseline tumor assessments or discontinue due to toxicity or clinical progression prior to post-baseline tumor assessments. The study plans to enroll 25 subjects to ensure 21 would be evaluable for the primary efficacy endpoint.

There is no reliable historical control data documenting response rates and disease control rates with chemotherapy or any other agent in ASQ. Previous clinical trials of single agent checkpoint inhibitors in pancreatic cancer have reported 0% ORR (anti-PD1, PDL1, CTLA4)²⁻⁶. A recent trial investigating anti-PDL1 combined with anti-CTLA4 therapy or anti-PD-L1 alone in metastatic PDAC reported ORR of 3.1% and 0% with the combination and single agent, respectively. This trial also reported a median PFS of 1.5 months in both cohorts, DCR at 3 months of 9.4% and 6.1% and PFS rate at 6 months of 9.4% and 3.6% in the combination and single agent cohorts, respectively⁵. Given the results of these trials, the phenomenon that immunotherapy often has a delayed effect compared to chemotherapy and ASQ being an aggressive disease with limited treatment options the primary endpoint of this study will be a 30% DCR at four months.

13.2 Data and Analysis Plan

Analysis of Primary Endpoint

The primary endpoint of the study will be disease control (DC) at four months using RECIST 1.1. DC is defined as complete response, partial response and stable disease at 4 months, per RECIST 1.1. Disease control rate (DCR) will be estimated as the proportion of patients who achieve DC at 4 months, along with 95% confidence interval

Analysis of Secondary Clinical Endpoint

The objective response rate defined as the proportion of response evaluable subjects who have a complete response (CR) or partial response (PR) using RECIST 1.1 criteria at any time during the study. The evaluable population includes all subjects who have completed at least one dose of retifanlimab and have received at least one follow-up scan or discontinue due to toxicity or clinical progression prior to post-baseline tumor assessments. Response rate will be reported with exact 95% confidence interval.

Progression-free Survival (PFS) is defined as the time from cycle 1, day 1 of retifanlimab until first documented local progression or death due to any cause. Disease progression will be assessed using RECIST (version 1.1) and/or documented clinical progression as assessed by the treating provider. Due to the expectation that some patients may experience delayed clinical responses to therapy, patients with disease progression by radiographic imaging or laboratory parameters during a 12-week evaluation period but without rapid clinical deterioration or significant change in performance status that requires additional immediate therapy may continue to receive treatment on study. Subjects that meet the above criteria and continue on study therapy must discontinue treatment upon documentation of disease progression on the second scan. The date of progression will be backdated to the time of first RECIST criteria progression. Tumor assessments will be made using RECIST 1.1 and immune RECIST (iRECIST). Individuals will be censored at the date of the last scan prior to initiation of an alternative therapy for PFS if no event occurs before the start of the alternative therapy.

PFS will be summarized descriptively using the Kaplan-Meier method. Analysis of PFS will be restricted to evaluable individuals who complete at least one dose of retifanlimab.

Analysis of Safety Endpoints

The safety analysis will be performed in all subjects who receive at least one dose of study drug. A baseline measurement and at least 1 laboratory or other safety-related measurement obtained after at least 1 dose of study treatment may be required for inclusion in the analysis of a specific safety parameter (e.g., lab shifts from baseline). A complete list of all AE data will be provided along with an assessment of NCI CTCAE grade and relationship to study drug. The incidence of AEs will be tabulated by subgroups of interest (e.g. grade 3 or higher, organ class, relationship to study drug). For analyses at the individual level, the highest grade and relationship to study drug will be assumed if multiple events have occurred. Toxicity will be tabulated by type and grade and will be summarized with descriptive statistics. Other safety data will be assessed in terms of

physical examination, clinical chemistry, hematology, vital signs, and ECGs. Negative binomial regression and Cox proportional hazards models will be used to assess the rate of AE and time to first toxicity, respectively.

Exploratory Clinical Analysis

Overall survival is defined as the duration of time from start of study treatment to time of death. For subjects lost to follow-up or whose vital status is unknown, every effort will be made to determine the date such subjects were last known to be alive. Such efforts may include phone calls, certified mail, and the checking of public records. Subjects who are alive or lost to follow-up as of the data analysis cutoff date will be right-censored. The censoring date will be determined from the date the subject was last known to be alive.

OS will be summarized descriptively using the Kaplan-Meier method. Analysis of OS will be restricted to evaluable individuals who complete at least one dose of retifanlimab. Median event-free survival will be reported and the associated 95% confidence interval will be estimated.

DOR and TTP were defined in second 11.3.

Exploratory Biomarker Analysis

To specifically evaluate the impact of therapy on the tumor microenvironment, we will compare biopsies obtained at baseline vs. after two cycles of retifanlimab (refer to section on Trial Design). In addition, immune effector cell phenotype circulating in peripheral blood will be assessed. Exploratory data analyses will include plots and summary statistics of these immunologic correlative markers at baseline as well as at the various time points. Patterns of change in the longitudinal data on these markers will be evaluated in this manner for each of the correlative outcomes of interest. Exploratory analyses can also be conducted to examine potential differences in various immune biomarkers between patients who have disease control (prolonged SD or any response vs. those with progressive disease). Linear mixed models can also be used to explore differences in these markers between the two outcome groups along with graphical analyses that plot marker values across time for the two groups to assess potentially different patterns of change between these groups. Appropriate transformations of the various correlative markers will be used in the presence of skewed data distributions.

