1.4 Study Design

This is multi-center two stage phase 2 study to evaluate the clinical activity of retifanlimab in patients with unresectable or metastatic ASQ. This study will enroll subjects who have progressed after at least 1 prior chemotherapy regimen, have been deemed unfit for cytotoxic chemotherapy or who have refused cytotoxic chemotherapy. The primary endpoint of this study will be disease control rate (DCR) at 4 months following the start of treatment using RECIST 1.1. Up to 25 subjects will be enrolled to target 21 evaluable patients.

The study will consist of a screening period (within 21 days of first dose), a treatment period per the table below (**Section 10**), and a follow-up period. Subjects will receive a baseline biopsy and then be treated with the anti-PD1 antibody retifanlimab every 4 weeks. After 2 doses (8 weeks), subjects will be assessed for response with imaging and laboratory tests and receive another research biopsy. For patients with stable disease or tumor response and clinical benefit, retifanlimab will be continued until disease progression or unacceptable toxicity. Patients will be evaluated radiographically after every 2 doses of retifanlimab (every 8 weeks). Subjects will come

to the clinic for dosing and assessments on Day 1 of each cycle. Assessment will consist of 1) physician evaluation to assess symptoms of tumor response or progression and potential drug related toxicity, 2) cross sectional imaging (CT scans), 3) CA19-9 blood levels. Additional visits for safety and immune monitoring follow-up will occur per the study calendar in **Section 10**.

No dose escalations or reductions are allowed. Enrollment will continue until 21 subjects have received at least one dose of retifanlimab and completed one cycle of therapy. The null hypothesis that the DCR 4 months following the start of treatment is 5% will be tested against a one-sided alternative (DCR of 30%).

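### Does the 95% interval for the primary disease control rate conflict with the one-sided, count-based test?

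*Combined protocol and SAP*

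**What the plan says.** Section 13.1 sets out a Simon two-stage design: 7 patients first, a stop if none has disease control, otherwise 14 more. A null of 5% is "tested against a one-sided alternative of 30% disease control rate at 4 months". The decision is by count: "The null hypothesis (disease control rate of 5%) will be rejected if 3 or more patients with disease control at 4 months are observed" over both stages. On error rates it says: "This design yields a type I error rate of 0.064 (target type I error 0.1"), with power of 90% at a true rate of 30%.

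Section 13.2 covers estimation of the primary endpoint: "Disease control rate (DCR) will be estimated as the proportion of patients who achieve DC at 4 months, along with 95% confidence interval". It names no method, no link to the test and no allowance for the two stages. For the secondary objective response rate the same section is more specific: "Response rate will be reported with exact 95% confidence interval".

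**The concern.** Two things catch the eye.

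- **Level.** The test is one-sided with a 10% target, but the interval is 95%. At 3/21, the smallest successful result, the report would announce rejection of 5% beside a primary interval that contains 5%. A reader who took the interval as the criterion would in effect require 4/21, with type I error 1.6% and power 86.1% instead of 6.4% and 90.4%.
- **Method.** The primary endpoint is specified less fully than a secondary one. At 3/21 the 95% upper limit is 29.3% by Wald, 36.3% by Clopper-Pearson and 42.5% by a stage-wise exact interval, so the choice decides whether the 30% alternative lies inside. An ordinary exact interval also ignores the possible stop at 0/7.

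If the plan really left open which of the two decides, the success criterion could be argued over after the data were seen.

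**Working it through.** **Inputs (section 13.1).** n1 = 7, stop at 0/7; n2 = 14; reject at 3 or more of 21; null 5%, alternative 30%; one-sided target 0.1. From section 13.2: a 95% interval.

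**1. Reproduce the plan's figures.** With X1 ~ Bin(7, p) and X2 ~ Bin(14, p),

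P(reject) = P(X1=1)·P(X2≥2) + P(X1=2)·P(X2≥1) + P(X1≥3).

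- p = 5%: 0.25728 × 0.15299 + 0.04062 × 0.51233 + 0.00376 = 0.03936 + 0.02081 + 0.00376 = 0.0639 (plan: 0.064).
- p = 30%: 0.24706 × 0.95252 + 0.31765 × 0.99322 + 0.35293 = 0.23533 + 0.31550 + 0.35293 = 0.9038 (plan: 90%).
- Early stop at 5%: 0.95^7 = 0.698 (plan: 70%).

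The confidence interval enters none of these.

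**2. Where test and interval part.** The ordinary exact (Clopper-Pearson) lower limit at x/21 with lower-tail error a exceeds 5% only if P(Bin(21, 0.05) ≥ x) < a. At x = 3 this tail is 0.085. That is above 0.025, so the two-sided 95% interval includes 5%. It is below 0.10, so the one-sided 90% bound excludes 5%.

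| Result | Count rule | Exact 95% interval | Exact one-sided 90% lower bound |
|---|---|---|---|
| 2/21 | do not reject | 1.2% to 30.4% | 2.6% |
| 3/21 | reject | 3.0% to 36.3% | 5.4% |
| 4/21 | reject | 5.4% to 41.9% | 8.6% |

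The disagreement is confined to 3/21. At the level of the test, the ordinary exact bound excludes 5% exactly when the count rule rejects. The cause is the level and not the staging: the stage-wise 95% interval at 3/21 (3.4% to 42.5%) also includes 5%, as do the Wald, Wilson, Agresti-Coull and Jeffreys 95% intervals.

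**3. How often 3/21 occurs.** P(stage 2 reached and total = 3) is 4.8%, 14.5%, 17.5%, 13.9% and 4.2% at true rates of 5%, 10%, 15%, 20% and 30%.

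**4. Does ignoring the stages harm the ordinary exact interval?** Enumerate all outcomes, using n = 7 if stopped and n = 21 otherwise, for true rates from 1% to 95% in steps of 1%.

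- Up to 30%, coverage is at least 97.4%.
- Up to 41%, it is at least 95.3%.
- It falls below 95% only at 42% (93.9%) and 43% (94.0%), outside the 5% to 30% design range.

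**5. What a stage-wise interval would cost.**

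| Result | Ordinary exact 95% upper limit | Stage-wise 95% upper limit |
|---|---|---|
| 1/21 | 23.8% | 41.0% |
| 2/21 | 30.4% | 41.3% |
| 3/21 | 36.3% | 42.5% |

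After a failed 1/21 the stage-wise interval would still include the 30% target; the ordinary exact interval excludes it.

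**The case for a change.** The best case for a change is that borderline results are where readers most need clarity. Between true rates of 10% and 20%, 3/21 has probability of roughly 14% to 17%, and at 5% it makes up 0.048/0.064 = 75% of all rejections. No sentence says that the interval is descriptive, and naming a method alone would not remove the mismatch, because every 95% interval computed at 3/21 includes 5%. An unnamed method also leaves some room for choice after the data are seen: a Wald interval would first exclude 5% at 5/21.

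The arithmetic stands, and it is true that the section does not name the method. The inference does not. The error rates attached to 4/21 and 5/21 belong to tests that nobody planned; they arise only if a reader swaps the written rule for the interval. Nothing in the documents points to Wald, and the exact method named for the response rate in the same section is the natural one to carry across. The stage-wise interval is a defensible preference, but it is not needed to match the test, and it is much wider after failed results.

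**Conclusion.** The concern does not call for a change. Section 13.1 makes the count of 3 or more of 21 the criterion for rejection, and no section gives the interval a testing role. A two-sided 95% interval beside a one-sided 10% test is a difference of confidence level, seen here at the single outcome 3/21. Followed as written, the plan gives the same decision with the stated type I error (0.064) and power (90%).

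What remains is reporting detail that an analyst would fill sensibly: the exact method for DCR, and the understanding that the 95% interval describes precision. This rests on two assumptions: that the ordinary exact interval is used, as for the response rate, and that the stages enrol 7 and 14 evaluable patients as planned.

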1.3 Exploratory Objectives

- 1.3.1 To assess overall survival (OS).
- 1.3.2 To assess duration of response (DOR) and time to progression (TTP).
- 1.3.3 To assess the DCR, ORR, PFS, and DOR by immune RECIST (iRECIST).
- 1.3.4 To identify potential biomarker predictors of response versus resistance to retifanlimab and autoimmune toxicity in plasma samples.
- 1.3.5 To test for predictors of response and resistance and explore changes in the tumor microenvironment (TME) following retifanlimab treatment in collected archived tissue and pre- and post-treatment biopsies via immunohistochemical studies.
- 1.3.6 Measure tumor marker kinetics (CA 19-9) in subjects receiving treatment and correlate with OS, PFS, and best overall response.
- 1.3.7 Measure tumor mutation burden, microsatellite instability, and profile genetic abnormalities in treated patients and correlate with response and resistance to therapy.

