5.9.1 Disease Progression

Retifanlimab is expected to trigger immune-mediated responses, which require activation of the immune system prior to the observation of clinical responses. Such immune activation may take weeks to months to be evident. Some subjects may have objective volume increase of tumor lesions or other disease parameters within weeks following the start of immunotherapy. Such subjects may not have had sufficient time to develop the required immune activation or, in some subjects, tumor volume or other disease parameter increases may represent infiltration of lymphocytes into the original tumor. In conventional studies, such tumor volume or relevant laboratory parameter increases during the first 2-4 months of the study would constitute disease progression and lead to discontinuation of imaging to detect response, thus disregarding the potential for subsequent immune-mediated clinical response.

Subjects will be permitted to continue with treatment beyond initial RECIST 1.1 defined PD as long as they meet the following criteria:

- Investigator-assesses that the patient is not clinically deteriorating, and
- Subject is tolerating study drug.

The assessment of lack of deterioration should take into account whether the subject is clinically stable or if they unlikely to receive further benefit from continued treatment. The following criteria need to be taken into consideration:

- No significant decline in ECOG performance status.
- Absence of rapid progression of disease or of progressive tumor at critical anatomical sites (e.g., cord compression) requiring urgent alternative medical intervention.

All decisions to continue treatment beyond PD must be discussed with the IND Sponsor and documented in the study records.

Tumor assessments will be made using RECIST 1.1 (**Appendix B**) and iRECIST (**Appendix C**).

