5.9.2 Retreatment with Retifanlimab

Patients who stop retifanlimab with SD or better may be eligible for resume therapy if they progress after stopping retifanlimab and they meet the following criteria:

EITHER

• Stopped initial treatment with retifanlimab after attaining an investigator determined confirmed CR according to RECIST 1.1, was treated for at least 6 months with retifanlimab, and received at least two doses of retifanlimab beyond the date when the initial CR was declared.

OR

• Subject had SD, PR or CR and stopped retifanlimab treatment after 24 months of study drug for reasons other than disease progression or intolerability

AND

- Experienced an investigator-determined confirmed radiographic or clinical disease progression after stopping their initial treatment with retifanlimab
- Did not receive any anti-cancer treatment since the last dose of retifanlimab
- Have an ECOG performance status of 0-2
- Female subject of childbearing potential should have a negative urine or serum pregnancy test within 3 days prior to receiving retreatment with study medication.
- Female subjects of childbearing potential should be willing to follow instructions for method(s) of contraception or abstain from heterosexual activity for the course of the study through 6 months after the last dose of study drug.
- Male subjects should agree to use an adequate method of contraception starting with the first dose of study therapy through 6 months after the last dose of study therapy.
- Does not have a history or current evidence of any condition, therapy, or laboratory abnormality that might interfere with the subject's participation for the full duration of the trial or is not in the best interest of the subject to participate, in the opinion of the treating investigator.

Subjects who restart treatment should resume at the next cycle which they would have received prior to discontinuation. Study visit requirements are outlined in the Study Calendar (Section 10.0).

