11.2 Secondary Endpoints

The secondary endpoints are as follows:

- ORR is defined as the proportion of subjects with PR or CR according to RECIST 1.1. Subjects who discontinue due to toxicity or clinical progression prior to post-baseline tumor assessments will be considered as non-responders. Otherwise, subjects who discontinue or do not have any post-baseline scans for other reasons including withdrawal of consent or being lost to follow-up prior to C2D1 will be replaced and not included in the primary efficacy analysis.
- Progression-free survival (PFS) is defined as the number of months from the first
 dose of retifanlimab to radiographic disease progression (PD or relapse from CR
 as assessed using RECIST 1.1 criteria), documented clinical progression as
 assessed by the treating provider, or death due to any cause. PFS will be censored
 at the date of the last scan for subjects without documentation of disease
 progression at the time of analysis.
- Safety assessed by the following measures:
 - Number of patients who have grade 3 or above drug-related toxicities
 - Frequency of drug-related toxicity by grade
 - Retifanlimab-related infusion reactions
 - Immune-related AEs
 - Unacceptable toxicities
 - Vital signs: BP, pulse, temperature
 - Physical examination
 - Changes in ECG readings
 - Clinical hematology: complete blood count (CBC) with differential ANC,
 ALC, AEC, and platelet count
 - Clinical serum chemistry: sodium, potassium, chloride, bicarbonate, glucose, blood urea nitrogen (BUN), creatinine, lactate dehydrogenase (LDH), ALT, AST, alkaline phosphatase, lipase, bilirubin (total), total protein, albumin, calcium, magnesium and phosphate

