The best overall response is the best response recorded from the start of the treatment until disease progression/recurrence (taking as reference for progressive disease the smallest measurements recorded since the treatment started). The subject's best response assignment will depend on the achievement of both measurement and confirmation criteria.

For Subjects with Measurable Disease (i.e., Target Disease)

Target Lesions	Non-Target Lesions	New Lesions	Overall Response	Best Overall Response when Confirmation is Required*
CR	CR	No	CR	≥4 wks. Confirmation**
CR	Non-CR/Non-PD	No	PR	
CR	Not evaluated	No	PR	\geq 4 wks.
PR	Non-CR/Non-PD/not evaluated	No	PR	Confirmation**
SD	Non-CR/Non-PD/not evaluated	No	SD	Documented at least once \geq 4 wks. from baseline**
PD	Any	Yes or No	PD	
Any	PD***	Yes or No	PD	no prior SD, PR or CR
Any	Any	Yes	PD	

^{*} See RECIST 1.1 manuscript for further details on what is evidence of a new lesion.

Note: Subjects with a global deterioration of health status requiring discontinuation of treatment without objective evidence of disease progression at that time should be reported as "symptomatic deterioration." Every effort should be made to document the objective progression even after discontinuation of treatment.

Reference

E.A. Eisenhauer, P. Therasse, J. Bogaerts, L.H. Schwartz, D. Sargent, R. Ford, J. Dancey, S. Arbuck, S. Gwyther, M. Mooney, L. Rubinstein, L. Shankar, L. Dodd, R. Kaplan, D. Lacombe, J. Verweij. New response evaluation criteria in solid tumours: Revised RECIST guideline (version 1.1). Eur J Cancer. 2009 Jan;45(2):228-47.

^{**} Only for non-randomized trials with response as primary endpoint.

^{***} In exceptional circumstances, unequivocal progression in non-target lesions may be accepted as disease progression.

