Detection of Progression at Visits After Pseudo-progression Resolves

After resolution of pseudo-progression (i.e., achievement of iSD/iPR/iCR), iUPD is indicated by any of the following events:

Target lesions

O Sum of diameters reaches the PD threshold ($\geq 20\%$ and ≥ 5 mm increase from nadir) either for the first time, or after resolution of previous pseudo-progression. The nadir is always the smallest sum of diameters seen during the entire trial, either before or after an instance of pseudo-progression.

Non-target lesions

- o If non-target lesions have never shown unequivocal progression, their doing so for the first time results in iUPD.
- o If non-target lesions had shown previous unequivocal progression, and this progression has not resolved, iUPD results from any significant further growth of non-target lesions, taken as a whole.

New lesions

- o New lesions appear for the first time
- Additional new lesions appear
- o Previously identified new target lesions show an increase of ≥ 5 mm in the new lesion sum of diameters, from the nadir value of that sum
- o Previously identified non-target lesions show any significant growth

If any of the events above occur, the overall response for that visit is iUPD, and the iUPD evaluation process (see Assessment at the Confirmatory Imaging above) is repeated. Progression must be confirmed before iCPD can occur.

The decision process is identical to the iUPD confirmation process for the initial PD, except in one respect. If new lesions occurred at a prior instance of iUPD, and at the confirmatory scan the burden of new lesions has increased from its smallest value (for new target lesions, their sum of diameters is ≥ 5 mm increased from its nadir), then iUPD cannot resolve to iSD or iPR. It will remain iUPD until either a decrease in the new lesion burden allows resolution to iSD or iPR, or until a confirmatory factor causes iCPD.

Additional details about iRECIST are provided in the iRECIST publication²⁰.

Table 6: Comparison between RECIST 1.1 and iRECIST

	RECIST 1.1	iRECIST	
Definitions of disease: numbers, sites and target or non	Measurable are diameters greater than 10 mm (15 for nodes maximum of 5 (2 per organ)	No change from RECIST 1.1	
CR, PR or SD	Cannot have met criteria for progression	Can have had iUPD (more than once) but not iCPD before iCR, iPR or iSD	
Confirmation of CR or PR	Only in non-randomized studies	As per RECIST 1.1	
Confirmation of SD	Not required	As per RECIST 1.1	

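### The Section 13.2 window for the RECIST 1.1 ORR does not end at progression, which conflicts with Appendix B and Table 6 and lets a post-progression response be counted

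*Combined protocol and SAP*

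**What the plan says.** Section 13.2 (Analysis of Secondary Clinical Endpoint) defines the ORR numerator as evaluable subjects who "have a complete response (CR) or partial response (PR) using RECIST 1.1 criteria at any time during the study". Section 11.2 gives no window: "ORR is defined as the proportion of subjects with PR or CR according to RECIST 1.1". Section 13.2 is therefore the only place that sets a time window for ORR.

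The appendices set a narrower one. Appendix B states: "The best overall response is the best response recorded from the start of the treatment until disease progression/recurrence". In Appendix C, Table 6, the RECIST 1.1 entry for CR, PR or SD reads "Cannot have met criteria for progression". The iRECIST entry beside it reads "Can have had iUPD (more than once) but not iCPD before iCR, iPR or iSD". ORR by iRECIST is a separate exploratory objective (1.3.3) and endpoint (11.3).

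Scans after progression are foreseen. Section 5.9.1 says "Subjects will be permitted to continue with treatment beyond initial RECIST 1.1 defined PD", subject to conditions, and Appendix C calls for repeat imaging 4 to 8 weeks later. Under 5.9.2, certain patients who stopped with SD or better "may be eligible for resume therapy if they progress after stopping retifanlimab".

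**The concern.** Section 13.2 and the appendices can classify the same scans differently. An analyst who follows 13.2 literally looks for CR or PR on any scan during the study. One who follows Appendix B stops at first progression. Both could claim to have followed the plan, and they could report different ORRs.

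The situation can arise in practice. Section 5.9.1 explains that imaging continues after early tumor growth so that a later immune-mediated response is not missed, and 13.2 itself expects some delayed responses. Within 13.2 the PFS rule is bounded: progression is backdated to the first RECIST progression, and follow-up is censored before alternative therapy. The ORR rule has no such bound.

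Three things are at stake: whether the RECIST ORR includes responses that Table 6 allows only under iRECIST, whether ORR and PFS for the same patient are coherent, and whether DOR can be calculated for every counted responder.

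**Working it through.** **1. One patient under each rule.** Let *s* be the baseline sum of target diameters. At week 8 the sum is at least 1.20*s* and at least 5 mm above *s*, with no new lesion and no non-target progression. Appendix B calls this PD. The repeat scan does not confirm progression and treatment continues. At week 24, a scheduled scan on the 8-weekly calendar, the sum is at most 0.70*s*, which meets the PR size threshold.

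| Rule | Week 8 | Week 24 | Result |
|---|---|---|---|
| 13.2 ORR, read literally | PD | PR | Responder |
| Appendix B best overall response | PD, window closes | Not considered | Best response PD |
| Table 6, RECIST 1.1 | Progression met | PR not available | Not a responder |
| Table 6, iRECIST | iUPD | iPR | iRECIST responder |
| 13.2 PFS | Event | – | PFS event at week 8 |

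The example needs progression without a new lesion. Under the Appendix B table, a new lesion makes the overall response PD whatever the target lesions show. A patient whose new lesion persists is therefore not a RECIST responder at week 24 under any window.

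**2. Duration of response.** Section 11.3 measures DOR from first documented response to progression. With response at week 24 and progression at week 8, DOR = 8 − 24 = −16 weeks. Using a later progression date instead would give DOR and PFS different progression dates for one patient, and no rule in the plan provides for that.

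**3. Size.** The plan states no figure for ORR. Section 13.1 targets 21 evaluable patients and 13.2 specifies an exact 95% interval. One patient is 1/21 = 4.8 points. Clopper-Pearson limits are the 0.025 quantile of Beta(*x*, *n*−*x*+1) and the 0.975 quantile of Beta(*x*+1, *n*−*x*). For 0/21 the upper limit is 1 − 0.025^(1/21) = 16.1%.

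| Responders counted | ORR | Exact 95% CI |
|---|---|---|
| 0/21 | 0% | 0 to 16.1% |
| 1/21 | 4.8% | 0.1 to 23.8% |
| 2/21 | 9.5% | 1.2 to 30.4% |
| 3/21 | 14.3% | 3.0 to 36.3% |

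The range 0 to 3 is an assumption. The documents do not say how many such patients to expect.

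**4. Primary design.** Section 13.1 stops at 0/7 and rejects at 3 or more of 21. The rejection probability is the sum over *x* = 1 to 7 of P(X1 = *x*) × P(X2 ≥ 3 − *x*), with X1 ~ Bin(7, *p*) and X2 ~ Bin(14, *p*). At *p* = 0.05 this is 0.0639 (stated 0.064). At *p* = 0.30 it is 0.904 (stated 90%). Early stopping under the null is 0.95^7 = 0.698 (stated 70%). All three reproduce, and none uses ORR.

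**5. Retreatment.** Patients who stopped with CR or PR are normally counted as responders already. The only route by which retreatment adds a responder is a patient who stopped at 24 months with SD, progressed off treatment, and then responded on retreatment.

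**The case against.** The best defence is that the 13.2 phrase itself invokes RECIST 1.1 criteria, and the protocol's own version of those criteria excludes a CR or PR after progression. On that view the at-any-time wording only contrasts ORR with the 4-month landmark used for disease control in the paragraph before. Post-progression responses have their own place in the iRECIST ORR. For patients who have stopped treatment, disease imaging ends at progression (1.4, 5.12.2), which narrows the exposure. ORR is secondary, with no test or threshold.

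Much of this stands. A reader might infer that the plan directs post-progression responses into the RECIST ORR. It does not: no sentence says so, and the narrow reading is available. What the defence does not remove is that the only stated ORR window is wider than the appendices allow, in a plan that expects delayed responses and bounds PFS explicitly.

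Three further inferences also go too far:
- Retreatment is not a main route, as step 5 of the working shows.
- Loss of comparability with the ORRs of 0% and 3.1% cited in 13.1 cannot be claimed, because the plan does not say which criteria or window those trials used.
- The RECIST and iRECIST ORRs would not become identical even on the wide reading, since iRECIST still bars a response after confirmed progression.

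**Conclusion.** The concern holds as a conflict between a stated window and the criteria it relies on. Read literally, 13.2 can count a response after RECIST 1.1 progression, while Appendix B and Table 6 do not allow it. The main route is treatment and imaging beyond progression.

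Each affected patient moves the RECIST ORR by 4.8 points, assuming 21 evaluable patients. The first would take it from 0% to 4.8%, and that patient would also have a negative or undefined DOR. The number of such patients is unknown and may be zero. The primary endpoint, sample size and decision rule do not change. The point concerns when a response may occur and does not depend on whether responses need confirmation.

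**What to change.** In 13.2, replace the at-any-time window with: best overall response of CR or PR from first dose until first RECIST 1.1 progression, per Appendix B. Mirror this in 11.2. Add that responses first seen after RECIST progression count only in the iRECIST ORR, and apply the same window to RECIST DOR in 11.3. Any response on retreatment can be listed separately.

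Ending the window also at the start of other anticancer therapy is an optional addition. It would match the PFS censoring rule in 13.2, but Appendix B does not require it.

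The cost is a sentence or two in 13.2, one in 11.2 and a clause for DOR. No new data are needed. Compared with the literal reading, the reported RECIST ORR can only stay the same or fall. The change is best made before responses are known, so that the choice of window cannot appear driven by results.
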